## 1. OBJECTIVES

### 1.1 Study Design

This is a 2-arm, randomized, double-blinded multi-center phase II trial to estimate the cumulative incidence of venous thromboembolic events (VTE) and major hemorrhage in hospitalized cancer patients receiving enoxaparin thromboprophylaxis. Hospitalized cancer patients considered to be at high risk of thrombosis (based on malignancy diagnosis and Padua risk factors) will be randomized to standard dose enoxaparin daily versus weight-adjusted enoxaparin daily for up to 14 days.

### 1.2 Primary Objectives

- The primary objectives of the study are to estimate the cumulative incidence of VTE and major hemorrhage in hospitalized cancer patients receiving standard dose or weight-adjusted enoxaparin.

### 1.3 Exploratory Objectives

- Compare rates of symptomatic VTE between enoxaparin arms at day 14
- Evaluate the performance of clinical scoring models (ie. Padua, IMPROVE, and Khorana Score) in predicting thrombotic risk in hospitalized cancer patients
- Assess the prognostic value of biomarkers (e.g. D-dimer and microparticles) to predict thrombosis in hospitalized cancer patients

## 2. BACKGROUND

### 2.1 Study Disease(s)

Venous thromboembolism is estimated to account for up to 5% of all deaths during hospitalization.[1] Recognizing the burden on healthcare and the preventable nature of venous thromboembolic events during hospitalization, U.S. Government agencies are working to improve the rates of prescribed thromboprophylaxis. The Agency for Healthcare Research and Quality identified thromboprophylaxis as the number one patient safety practice[2], the Surgeon General issued a *Call to Action*[3], and the Centers for Medicare & Medicaid Services is targeting hospital thromboprophylaxis in a national health-care quality initiative. Major professional organizations including the American Society of Clinical Oncology, National Comprehensive Cancer Network, American College of Chest Physicians, and European Society of Medical Oncology have all issued strong recommendations for the prescription of pharmacologic thromboprophylaxis of hospitalized cancer patients.[4-7] And yet, despite the association between cancer-thrombosis and increased in-hospital cancer mortality, the absolute benefit, toxicity and even appropriate dosing of routine thromboprophylaxis in cancer patients is unknown. In the three phase III registration trials comparing low molecular weight heparins with placebo in hospitalized medical patients, only 6% of patients carried a diagnosis of cancer and there was no statistical benefit for thromboprophylaxis in the subgroup analysis of cancer patients included in these trials.[8] This phase II trial will establish point estimates on the risk of

VTE and hemorrhage in preparation for a planned phase III clinical trial to assess the risks and benefits of anticoagulation in cancer patients at increased risk for thrombosis.

### **Risk factors for thrombosis in hospitalized cancer patients**

In analysis of a large hospital discharge database that included over 1 million cancer patients, the overall incidence of venous thromboembolic events (VTE) was 4.1% per hospitalization with considerable variation according to presence of concomitant thrombotic risk factors.[9] For instance, in 26,118 patients with pancreatic cancer the rate of VTE was 8.1% per hospitalization whereas the rate was 1.4% in the 50,898 patients with head and neck malignancy. Other higher risk tumors included ovary (5.6% rate of VTE), lung (5.1%), stomach (4.9%), and non-Hodgkin lymphoma (4.6%). Independent risk factors for thrombosis during hospitalization included primary site of cancer, age, chemotherapy, and comorbidities (e.g. infection, pulmonary, renal disease).

Prediction models have been developed to identify which populations of hospitalized patients are at highest risk of thrombosis but these have not been specifically developed for hospitalized cancer populations. In the widely cited Padua Prediction Score, independent risk factors for VTE include cancer, prior history of VTE, reduced mobility, hereditary thrombophilia, recent surgery or trauma, obesity, elderly, and comorbidities (e.g. infection, acute coronary syndrome, respiratory failure).[10] Among the 659 low risk patients (Padua Score of <4) not receiving pharmacologic thromboprophylaxis, only one patient (0.2%) was diagnosed with VTE during hospitalization. By comparison, the rate of thrombosis was 7.5% among the 469 high-risk patients (Padua Score  $\geq 4$ ).

### **Risk-benefit assessment for thromboprophylaxis for hospitalized cancer patients**

In a recent systematic review and meta-analysis of cancer patients enrolled in randomized phase III clinical trials.[8] Only 307 cancer patients were enrolled among the three major registration clinical trials involving low molecular weight heparins (or fondaparinux) versus placebo. The pooled relative risk of VTE was 0.91 (95% CI, 0.21-4.0) with two trials demonstrating a non-significant reduction of thrombosis in cancer patients while the third trial demonstrated a statistically significant increase in thrombosis in patients receiving thromboprophylaxis with fondaparinux. Fondaparinux has been shown previously in randomized clinical trials to prevent thrombosis following cancer surgery and thus these results are unlikely to point simply to the ineffectiveness of a single thromboprophylactic agent. In all studies the incidence of thrombosis was higher in the cancer subgroup receiving thromboprophylaxis compared with non-cancer patients. It is evident that anywhere from 1 in 5 to 1 in 20 hospitalized cancer patients are diagnosed with VTE despite receiving recommended thromboprophylaxis.

## **2.2 Study Agent (Enoxaparin)**

Enoxaparin is a low molecular weight heparin with antithrombotic properties approved by the Federal Drug Administration for prevention of deep vein thrombosis following abdominal or orthopedic surgery and in medical patients with restricted mobility during acute illness.

Enoxaparin administered subcutaneously achieves steady-state activity levels predicted by single-dose pharmacokinetics. After repeated subcutaneous administration of 40mg once daily,

the steady state is reached on day 2 with an average exposure ratio of 15% higher than after a single dose. Enoxaparin is primarily metabolized in the liver by desulfation and/or depolymerization to lower molecular weight species with much reduced biological potency. Renal clearance of active fragments represents about 10% of the administered dose and total renal excretion of active and non-active fragments 40% of the dose. In the elderly, the apparent clearance of enoxaparin following multiple subcutaneous doses is similar to younger subjects. A linear relationship exists between activity and creatinine clearance.

Standard dose enoxaparin for thromboprophylaxis in medical patients:

In a double blind multicenter parallel group study, enoxaparin at 20mg or 40mg once a day for 14 days was compared to placebo in medical patients with severely restricted mobility.[11] Patients were enrolled with the following diagnosis: congestive heart failure (NYHA class III or IV), acute respiratory failure or complicated chronic respiratory insufficiency, acute infection, or acute rheumatic disorder. A total of 1073 patients were treated on the study for a maximum of 14 days (median 7 days). Enoxaparin administered at 40mg once daily was associated with a significant reduction in thromboembolic events compared with placebo (5.5 vs 14.9, P<.001). The lower (20mg) dose of enoxaparin was not associated with a reduction in thromboembolic events (12.2%). Enoxaparin (40mg) was well tolerated with 6 of 360 patients suffering a major hemorrhagic event compared with 4 of 362 treated with placebo. There were 8 cases of thrombocytopenia in the placebo group and 2 in the enoxaparin (40mg) treated group. There were no significant differences in the groups for any other adverse outcomes.

Modified dose enoxaparin thromboprophylaxis in cancer patients:

The pharmacokinetic profile of low molecular weight heparins are known to be dependent on body weight.[12] Compared with fixed dose enoxaparin at 40mg, weight adjusted dose of enoxaparin of 1mg/kg yields significantly greater peak anti-Xa activity, anti-IIa activity and inhibition of thrombin generation.[12, 13] Notably, there is randomized trial data to support the safety and efficacy of enoxaparin at 1mg/kg daily for thromboprophylaxis in cancer patients. The CONKO-004 trial randomized over 300 patients with advanced pancreatic cancer to chemotherapy alone or chemotherapy with enoxaparin 1mg/kg daily for 3 months. At 3 months, they observed an approximate 85% risk reduction in the incidence of VTE in the arm randomized to intermediate dose enoxaparin (P=0.001) without an increase in major hemorrhage (P=1.0).[14]

### **2.3 Rationale**

Based on the available evidence, it is apparent that an accurate assessment of risk versus benefit for primary thromboprophylaxis of hospitalized cancer patients is not possible. It is also evident that hospitalized cancer patients commonly receive pharmacologic thromboprophylaxis without attention to the presence or absence of thrombotic risk factors. In highest risk cancer patients, current pharmacologic regimens are inadequate with as many as 20% patients suffering from thromboembolic events. The principle goals of this phase II clinical trial are to establish a more accurate point estimate of rate of VTE in high risk cancer patients receiving standard, fixed-dose low molecular weight heparin thromboprophylaxis and to develop a point estimate of hemorrhage using intermediate-dose enoxaparin prophylaxis in higher risk patients.

## 2.4 Correlative Studies Background

**Evaluation of Padua, IMPROVE, and Khorana risk models in hospitalized cancer patients.** Published risk models have been developed to identify a collective group of risk factors that identify patient populations considered to be at sufficiently high risk of thrombosis to warrant thromboprophylaxis. The IMPROVE scoring model was developed using a database of 15,000 patients from 12 countries. A multiple regression analysis identified independent risk factors for VTE in acutely ill hospitalized medical patients.[15] The incidence of thrombosis following hospitalization was 11% in patients with IMPROVE scores  $\geq 5$ . The four independent risk factors at admission comprising the scoring model are: previous history of VTE (3 points), known thrombophilia (3 points), age  $> 60$  years (1 point), and cancer (1 point). The Khorana score was developed for cancer outpatients receiving chemotherapy. Abnormal pre-chemotherapy complete blood count indices (white blood cell  $> 11 \times 10^9/L$ , hemoglobin  $< 10 \text{ g/dL}$ , and/or platelet count  $> 350 \times 10^9/L$ ) are independently associated with thrombosis in cancer outpatients and are elements of the Khorana risk score.[16-18] In order to evaluate the performance of the Khorana score in predicting thrombotic risk for hospitalized cancer patients, we will calculate the Khorana score utilizing laboratory data (e.g. blood counts) upon admission. The Khorana score will be calculated for all patients following completion of the study during the data analysis phase. As this scoring system was not specifically developed for cancer patients, we will explore whether improved specificity can be achieved while retaining sensitivity to identify patients at greatest risk for VTE.

### **Microparticles and risk of thrombosis in cancer patients.**

Microparticles are vesicular structures measuring less than  $1 \mu\text{m}$  in size and are derived from a number of cells within the vascular compartment including leukocytes, platelets, red blood cells, and endothelial cells.[19] Initial interest in exploring the association between tissue factor bearing microparticles and thrombosis was based on observations that tissue factor bearing microparticles bind to a developing thrombus and play a role in fibrin propagation in vivo.[20] Utilizing an impedance-based flow cytometer specifically modified for microparticle measurement, we observed that tissue factor bearing microparticles are elevated in cancer patients diagnosed with VTE (adjusted OR 3.72,  $P=0.01$ ) and appear to be derived from the underlying tumor.[21] The association between tissue factor bearing microparticles and cancer associated thrombosis has now been reported by several groups, including in a mouse model of vascular injury.[22-25] A randomized, multi-center phase II clinical trial (MicroTEC Trial) substantiated the prognostic role of tissue factor bearing microparticles and VTE in cancer patients.[26] The cumulative incidence of VTE in cancer patients with elevated tissue factor bearing microparticles randomized to observation was 27% compared with 5% in those receiving enoxaparin (Gray's test  $P=0.06$ ) while 7.2% of those cancer patients with low levels of tissue factor bearing microparticles were diagnosed with VTE without thromboprophylaxis. Notably, the cumulative incidence of VTE was 43% at 2 month in patients with both elevated levels of D-dimer and tissue factor bearing microparticles compared with 4.2% for all other study subjects (Gray's test  $P$  value = 0.0001).[26] Planned correlative studies include the measurement of tissue factor bearing microparticles as well as the population of tissue factor bearing microparticles co-expressing P-selectin glycoprotein 1(PSGL-1).

### **3. PARTICIPANT SELECTION**

#### **3.1 Eligibility Criteria**

3.1.1 Participants must have histologically or cytologically confirmed diagnosis of solid tumor malignancy, lymphoma, or multiple myeloma

3.1.2 Cancer diagnosis or received treatment (chemotherapy or radiotherapy) for malignancy within the previous 6 months

3.1.3 One or more Padua-based risk factor:

- History of previous venous thromboembolic event (excluding superficial vein thrombosis)
- Reduced mobility (ECOG performance status 3 or 4, see Appendix A)
- Established hereditary thrombophilia (e.g. Factor V Leiden, G20210 prothrombin mutation, protein C or S deficiency, antithrombin deficiency).
- Recent surgery within the last 30 days
- Age  $\geq$  70 years
- Congestive heart failure (NYHA class III or IV)
- Complicated respiratory insufficiency (defined as an increased requirement for supplementary oxygen of at least 2L)
- Acute myocardial infarction or ischemic stroke
- Obesity (BMI  $\geq$  30)
- Receiving hormonal agents (e.g. tamoxifen, estrogen, testosterone)
- Acute infection (i.e. requiring antimicrobial therapy)

3.1.4 Age  $\geq$  18 years

3.1.5 Life expectancy of greater than 30 days

3.1.6 Platelet count  $\geq$  100,000/mcL

3.1.7 Creatinine  $<$  1.5 mg/dL or estimated creatinine clearance  $\geq$  50 mL/min/1.73 m^2

3.1.8 Ability to understand and the willingness to sign a written informed consent document

3.1.9 Weight between 50kg to 130 kg.

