## **4. REGISTRATION PROCEDURES**

### **4.1 General Guidelines for DF/HCC and DF/PCC Institutions**

Institutions will register eligible participants with the DF/HCC Quality Assurance Office for Clinical Trials (QACT) central registration system. Registrations must occur prior to the initiation of protocol therapy. Any participant not registered to the protocol before protocol therapy begins will be considered ineligible and registration will be denied.

An investigator will confirm eligibility criteria and a member of the study team will complete the QACT protocol-specific eligibility checklist.

Following registration, QACT office will perform randomization to Arm A or Arm B of enoxaparin. Randomization arm will be communicated directly through QACT to the research pharmacy at Beth Israel Deaconess Medical Center. For participants enrolled at Cleveland Clinic, a representative from the BIDMC Research Pharmacy will forward the randomization assignment to the dedicated contact at the Cleveland Clinic Research Pharmacy.

Issues that would cause treatment delays should be discussed with the Overall Principal Investigator (PI). If a participant does not receive protocol therapy following registration, the participant's registration on the study must be canceled. Notify the QACT Registrar of registration cancellations as soon as possible.

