#### **4.3 General Guidelines for Other Investigative Sites**

Eligible participants will be entered on study centrally at Beth Israel Deaconess Medical Center by the Study Coordinator.

Following registration, participants should begin protocol therapy within 24 hours. Issues that would cause treatment delays should be discussed with the Overall PI. If a participant does not

receive protocol therapy following registration, the participant's registration on the study must be canceled and they will be replaced. The Study Coordinator should be notified of cancellations as soon as possible.

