**5.2 Pre-Treatment Criteria**

In order to proceed with day 1 administration of enoxaparin, platelet count must be  $\geq 50,000/\mu\text{l}$  and CrCl must be  $>/= 50 \text{ ml/min}$ . All other laboratory assessments performed within 48 hours of enrollment may be used to determine eligibility and do not need to be repeated.

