#### **5.6 Criteria for Taking a Participant Off Protocol Therapy**

Cessation of enoxaparin and withdrawal from the study is mandated for the following reasons:

- Grade 3 or 4 hemorrhage and/or
  - Symptomatic hemorrhage in a critical area or organ such as intracranial, intraspinal, intraocular, retroperitoneal, intra-articular or pericardial, or intramuscular with compartment syndrome, and/or hemorrhage causing an acute fall in hemoglobin  $\geq 2\text{g/L}$  or hemorrhage leading to a transfusion of  $\geq 2$  units of packed red blood cells.
- Development of confirmed heparin induced thrombocytopenia
- Proximal deep vein thrombosis or pulmonary embolism
- Condition requiring therapeutic anticoagulation or dual antiplatelet therapy
- Renal failure (see section 6)
- Participant decides to withdraw from the protocol therapy
- General or specific changes in the participant's condition render the participant unacceptable for further treatment in the judgment of the treating investigator

Participants will be removed from the protocol therapy when any of these criteria apply. The reason for removal from protocol therapy, and the date the participant was removed, must be documented in the case report form (CRF). Alternative care options will be discussed with the participant.

A QACT Treatment Ended/Off Study Form will be filled out when a participant is removed from protocol therapy. This form can be found on the QACT website or obtained from the QACT registration staff.

In the event of unusual or life-threatening complications, treating investigators must immediately notify the Overall PI:

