### **Renal Failure**

CrCl (ml/min)	Arm A (standard enoxaparin)	Arm B (adjusted dose enoxaparin)
>40	No change	No change
30-40	No change	DECREASE to 40 mg daily
<30	HOLD	HOLD

Creatinine will be monitored at each study visit and as part of routine medical care. Enoxaparin

will be held for acute renal failure ( $\text{CrCl} < 30 \text{ml/min}$ ) diagnosed at any point during the study.

*Enoxaparin should be resumed when  $\text{CrCl}$  improves to  $\geq 40 \text{ml/min}$ .*

The  $\text{CrCl}$  can be estimated by either the Modification of Diet in Renal Disease (MDRD) which can be found at [http://www.kidney.org/professionals/KLS/gfr\\_calculator.cfm](http://www.kidney.org/professionals/KLS/gfr_calculator.cfm) or Cockcroft-Gault equation (below)

Men:

$$\text{CrCr (mL/min)} = \frac{(\text{140} - \text{age}) \times \text{body weight [kg]}}{\text{Cr [mg/dL]} \times 72}$$

Women:  $\text{CrCl (mL/min)} = \text{CrCl (as above)} * 0.85$

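### Criterion 3.1.7 lets patients be randomized on creatinine alone whom section 5.2 then bars from the first dose; sections 5.6 and 6 conflict on renal failure

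*Combined protocol and SAP*

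**What the plan says.** **Entry and first dose**

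- Section 3.1, criterion 3.1.7: creatinine below "1.5 mg/dL or estimated creatinine clearance" of at least 50 mL/min/1.73 m². Either limb is enough.
- Section 5.2: "In order to proceed with day 1 administration of enoxaparin, platelet count must be" at least 50,000/µl "and CrCl must be" at least 50 ml/min. Of the remaining tests it says: "All other laboratory assessments performed within 48 hours of enrollment may be used to determine eligibility and do not need to be repeated".
- Section 4.1: "Following registration, QACT office will perform randomization to Arm A or Arm B of enoxaparin". The study calendar (section 10) places randomization in the screening column and marks creatinine at both screening and day 1.
- Sections 4.1 and 4.3: a registered patient who gets no study drug is cancelled. Only 4.3, for other investigative sites, adds replacement: "registration on the study must be canceled and they will be replaced".
- Sections 5.1, 13.2 and 13.7.2: a patient counts as evaluable only after at least one dose.

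**Renal failure on treatment**

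- Section 5.6: "Cessation of enoxaparin and withdrawal from the study is mandated for the following reasons". Renal failure is on the list that follows, with a pointer to section 6.
- Section 6: enoxaparin "will be held for acute renal failure" (clearance under 30 ml/min) and is to be resumed once clearance is back to 40 or more. For renal function the section has only no-change, reduce, hold and resume rules.
- Section 5.7 follows patients to their last scheduled visit. Section 5.8 takes a patient off study only for loss of contact, withdrawn consent to data, or death.

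**The concern.** The entry criterion and the first-dose criterion are not the same test, and the stricter one is applied after allocation. A patient can therefore be properly eligible and randomized, then be refused drug because of a value the site already held at screening. Nothing in the patient's condition need have changed. Each such patient uses an allocation in a 50-patient trial stratified into six cells (two hospitals by three cancer-risk groups) and adds nothing to the estimates that the trial exists to supply.

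The renal-failure conflict bears on a different step. One section tells the site to stop drug and withdraw the patient from the study; another tells it to pause and restart. If sites read this differently, they may also differ on whether the patient keeps the day 14 assessment (both arms) and the day 17 ultrasound (Arm A only), which supply the primary endpoints.

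**Working it through.** No stated sample size, power or error rate is in dispute. The check asks whether patients exist who satisfy 3.1.7 and fail 5.2 on the same blood sample, and then what that costs.

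**Inputs.** Cockcroft-Gault as printed in section 6: CrCl = (140 − age) × kg / (72 × creatinine), times 0.85 for women. Permitted weight is 50 to 130 kg (3.1.9). Age 70 or over is itself a qualifying risk factor (3.1.3). Weight and creatinine are recorded at screening.

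**Creatinine at which clearance equals 50**, from (140 − age) × kg × sex factor / (72 × 50):

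- Woman, 70 y, 60 kg: 70 × 60 × 0.85 / 3600 = 0.99 mg/dL
- Man, 70 y, 60 kg: 70 × 60 / 3600 = 1.17 mg/dL

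Above these values the patient fails 5.2 but still satisfies 3.1.7 until creatinine reaches 1.5.

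**Clearance at given values**

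| Patient | Creatinine | CrCl (ml/min) | 3.1.7 | 5.2 |
|---|---|---|---|---|
| Woman, 70 y, 60 kg | 1.4 | 35.4 | met | failed |
| Man, 70 y, 60 kg | 1.4 | 41.7 | met | failed |
| Woman, 80 y, 60 kg | 1.0 | 42.5 | met | failed |
| Woman, 70 y, 50 kg | 1.4 | 29.5 | met | failed |

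The last patient is eligible at entry yet already under section 6's hold level of 30. At age 70 and creatinine 1.4, the day 1 check fails below 50 × 72 × 1.4 / 70 = 72.0 kg for a man and 72.0 / 0.85 = 84.7 kg for a woman, well inside the permitted weights.

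**Equation and units.** Section 6 also allows MDRD, whose formula is not printed, so it was not computed. Entry is in mL/min/1.73 m² and day 1 in ml/min. The documents do not say which equation governs either check.

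**Cost in allocations.** The share q of randomized patients who fail on day 1 is not given. Randomizations needed to dose 50 are 50 / (1 − q), rounded up:

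| Assumed q | Calculation | Randomized |
|---|---|---|
| 2% | 50 / 0.98 | 52 |
| 5% | 50 / 0.95 | 53 |
| 10% | 50 / 0.90 | 56 |
| 20% | 50 / 0.80 | 63 |

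Without replacement, precision falls a little. The plan's exact 90% interval for 3 of 25 reproduces as 3.35% to 28.17% (printed as 3.3 to 28.2%). With three events among 23 dosed, it becomes 3.7% to 30.4%.

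**Renal failure, side by side.** Section 5.6 makes stopping and study withdrawal mandatory, then points to section 6. Section 6 has no renal discontinuation rule, so the pointer leads to a hold-and-resume instruction. Section 5.6's title and closing lines speak of leaving protocol therapy, while its opening line speaks of leaving the study. Renal failure is not an off-study reason in 5.8, and 13.7.2 assesses every dosed patient for the primary endpoints.

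**The case against.** The best defence is that this is untidy wording with little statistical consequence. A sensible site would calculate clearance from the screening creatinine and not register a patient who would fail. Where patients are replaced, the dosed number is kept. The analysis is estimation by arm, not a powered comparison. The check is the same in both arms, precedes dosing, and physicians and patients are blinded. On renal failure, the pointer can be read as making section 6 the operative rule, and 5.7, 5.8 and 13.7.2 already support continued follow-up.

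Much of this stands, and it rules out several stronger readings that a reader might infer:

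- **That the platelet limits conflict in the same way.** They do not. Entry requires at least 100,000 and day 1 at least 50,000, so day 1 is the looser test. It discards no one who meets entry on the same count, and section 6 covers the range between.
- **That the mismatch itself removes older, lighter patients.** The 5.2 threshold does that whenever it is applied. The mismatch only moves the loss to after allocation.
- **That the estimates are biased in a known direction.** Nothing in the documents shows this.
- **That patients with renal failure definitely lose their endpoint visits.** The follow-up sections say otherwise; the difficulty is that 5.6 contradicts them.

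The defence does not remove the core. No passage tells a site to apply the 5.2 clearance limit before registration, and the checklist is built on 3.1.7. Replacement is written only in 4.3; 4.1 says only that registration is cancelled. Deferring to section 6 does not explain why an item with no discontinuation rule sits on a list of mandatory withdrawals.

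**Conclusion.** The point holds as two internal inconsistencies worth correcting; neither invalidates the design.

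First, some patients satisfy 3.1.7 and fail 5.2 on the same screening creatinine, and the protocol discovers this after randomization. That they exist is shown under Cockcroft-Gault at ordinary ages, weights and creatinine values; MDRD was not tested. How many there are depends on a case mix the documents do not give. The range of 52 to 63 randomizations for 50 dosed rests on assumed shares of 2% to 20%. The consequence is lost allocations in a small stratified trial and, if 4.1 sites do not replace, slightly wider intervals.

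Second, 5.6 and section 6 give different instructions for renal failure, and the study-withdrawal wording in 5.6 disagrees with 5.7, 5.8 and 13.7.2. That last disagreement affects every item on the 5.6 list, not only renal failure.

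**What to change.** - Reconcile 3.1.7 with 5.2, stating one equation and one unit, so that no patient can meet entry and fail the day 1 check on the same value. Which threshold applies is for the clinical team.
- Require the renal check to be confirmed, and recorded on the eligibility checklist, before randomization is requested.
- State in 4.1 whether cancelled patients are replaced, to match 4.3, and report the number randomized but not dosed, by arm, with reasons.
- Reconcile the renal entry in 5.6 with section 6. The treatment rule is again a clinical decision.
- Reword the study-withdrawal phrase in 5.6 to agree with 5.7 and 5.8, so that stopping drug does not end the day 14 assessment (both arms) or the day 17 ultrasound (Arm A).

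The cost is protocol wording and a checklist change. Some patients would be screened out before allocation instead of after it. No change to sample size or analysis method is needed.
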